5.5.3.2 Other Secondary Efficacy Endpoints

5.5.3.2.1 TSC-associated Seizure Treatment Responders and TSC-associated Seizure Freedom

Blinded Phase:

The number of patients experiencing a $>25\%$ increase, ≥ 0 to $\leq 25\%$ increase, >0 to $<25\%$ reduction, ≥ 25 to $<50\%$ reduction, ≥ 50 to $<75\%$ reduction or $\geq 75\%$ reduction in TSC-associated seizure frequency from baseline during the treatment period will be summarized by treatment arm.

In addition to the key secondary endpoint, the proportion of patients considered treatment responders, defined as those with a $\geq 25\%$ or $\geq 75\%$ reduction in TSC-associated seizure frequency from baseline and the proportion of patients who are TSC-associated seizure free, defined as those with a 100% reduction in TSC-associated seizure frequency from baseline, during the treatment period, for patients who have not withdrawn from the trial

during the treatment period will be summarized by treatment arm and analyzed using a CMH test stratified by age as described in Section 5.5.3.1.1.

Additionally, the proportion of patients responding will be presented graphically, by treatment arm, by plotting the percent reduction against the cumulative proportion of patients achieving that level of reduction. The x-axis will be the percent reduction from baseline and the y-axis will be the proportion of patients with at least that amount of reduction, i.e. $y = \Pr(X \geq x)$.

Sensitivity analyses will be performed on the ITT analysis set, repeating the above analysis, using data for only the maintenance period, titration period, and during each 4 weeks of the maintenance period (Week 1 to 4, Week 5 to 8 and Week 9 to 12 of the 12 week maintenance period).

Analyses on the maintenance period, titration period and by each 4 weeks of the maintenance period will include only patients who have at least 7 days of seizure data within each period.

Open-label Extension:

Descriptive summaries described above for the blinded phase will be repeated for OLE periods.

5.5.3.2.2 Number of TSC-associated Seizure Free Days

Blinded Phase Only:

The number of TSC-associated seizure free days during each period will be based on 28 day averages and calculated as:

$$(\text{Number of seizure free days in the period} \div \text{Number of reported days in IVRS in the period}) \times 28$$

The change from baseline in TSC-associated seizure free days per 28 days will be analyzed for the treatment period using an ANCOVA approach. The model will include baseline and stratified age group as covariates and treatment arm as fixed factor.

The estimated least squares means, treatment difference, together with the 95% CIs and p-value will be presented.

The analysis will be repeated for the maintenance period.

5.5.3.2.3 Other Seizures

Blinded Phase:

For other seizures (see Section 5.1.3.8), summaries and analyses will be performed as per the primary endpoint (Section 5.5.2). Patients with no seizures during the baseline period, for a particular seizure type, will be excluded from the analysis of that seizure type.

Other seizure and total seizure responders and freedom will also be summarized and analyzed using the methods described in Section 5.5.3.2.1. However, the summaries and analyses during the maintenance and titration periods and during each 4 weeks of the maintenance period will be produced for total seizures only. Patients with no corresponding other seizures during the baseline period will be excluded from the analysis for other seizures.

Open-label Extension:

Descriptive summaries described above for the blinded phase will be repeated for OLE periods.

5.5.3.2.4 Quality of Life in Childhood Epilepsy (2–18 Years)

Blinded Phase:

The QOLCE is a parent-reported questionnaire that evaluates health related quality of life in children aged 2–18 years old. It contains 76 items with 16 subscales covering 7 domains of life function: Physical activities, social activities, cognition, emotional well-being, behavior, general health, and general quality of life.

All items in the questionnaire are rated on a 5-point or 6-point categorical scale. Based on the responses to the items in each domain, scores for 16 subscales are derived. The subscales are presented in Table 4.

Table 4 QOLCE Subscales

Subscale	Item Domains	Items Used
Physical Restrictions	Physical Activities	3.1 (a to j)
Energy/Fatigue	Physical Activities	3.2 (a,b)
Attention/Concentration	Cognition	5.1 (a,d,e,f,g)
Memory	Cognition	5.1 (j,k,l,m,n,o)
Language	Cognition	5.1 (p,q,r,s,t,u,v,w)
Other Cognitive	Cognition	5.1 (b,c,h)
Depression	Emotional Well-Being	4.1 (a,d,e,l)
Anxiety	Emotional Well-Being	4.1 (b,g,j,n,o,p)
Control/Helplessness	Emotional Well-Being	4.1 (c,f,h,i)
Self-esteem	Emotional Well-Being	4.1 (k,m,q,r,s)
Social Interactions	Social Activities	6.1 (c,f,h)
Social Activities	Social Activities	6.1 (a,e) and 6.2
Stigma Item	Social Activities	6.1 (i)
Behavior	Behavior	7.1 (a,c,f,g,h,l,j,k,l,m,o,q,r,s,t)
General Health Item	General Health	8.1
Quality of Life Item	Quality of Life	9.1

Items within each subscale will be coded and linearly transformed, according to the methods of Sabaz et al.¹, to a score of 0 to 100, where 0 represents the lowest or poorest category and 100 represents the highest level of functioning.

A subscale score is calculated for each subscale by computing the mean of the items within the subscale. An 'Overall Quality of Life Score' can be calculated by taking the mean of the subscale scores.

Individual items will be listed only. The subscale scores and the overall quality of life score, recorded at each visit, will be summarized, on a continuous scale, by treatment arm. The change from baseline will also be included.

The change from baseline to the end of treatment visit, for the overall quality of life score, and the attention/concentration, memory, language, other cognitive, social interactions and behavior subscale scores only, will be analyzed using analysis of covariance (ANCOVA). The model will include baseline and stratified age group as covariates and treatment arm as fixed factor.

The estimated least squares means, treatment difference, together with the 95% CIs and p-value will be presented. Exploratory analyses may also be performed on other subscale scores.

Missing data will be handled according to Section 5.1.1.2.1.

The QOLCE was to be completed for patients aged 2-18 years old only. The primary analysis will be based on all patients who have a completed questionnaire, regardless of age. Summaries and analyses will be repeated using questionnaires only from patients who were aged 2 to 18 years old at the time of informed consent.

The individual responses will not be listed, only the derived information for each derived score will be listed.

Open-label Extension:

Descriptive summaries described above for the blinded phase will be repeated for OLE visits.

5.5.3.2.5 Quality of Life in Epilepsy, Version 2 (19 Years and Above)

Blinded Phase:

The QOLIE-31-P is a survey of health-related quality of life for adults with epilepsy. It comprises 38 questions about health and daily activities and also includes questions designed to evaluate how much distress the patient feels about problems and worries related to epilepsy. The QOLIE-31-P will be administered to patients aged 19 years or older. Should the patient be unable to complete the QOLIE-31-P independently, it is permissible for their caregiver to assist.

The questionnaire consists of the following 7 subscales: energy, mood, daily activities, cognition, medication effects, seizure worry, and overall quality of life. Each subscale consists of a number of questions in addition to a 'distress' item. The raw score for each question and the 'distress' item are converted to a 0-100 score according to the scoring manual² (higher scores reflecting greater well-being). The converted scores for each question within the subscale are then used to calculate a final subscale weighted score (higher scores reflect better quality of life; lower ones, worse quality of life) as follows:

$$(\text{Sum of converted scores for each question in the subscale} \div \text{Number of questions in the subscale}) \times \text{'distress' item converted score}$$

The total score (ranging from 0 to 100) is then calculated as:

$$(\text{Sum of all subscale weighted scores} \div \text{Sum of all subscale 'distress' item converted scores}) \times 100$$

Individual items will be listed only. The weighted subscale scores and the total score, recorded at each visit, will be summarized, on a continuous scale, by treatment arm. The change from baseline will also be included.

The change from baseline to the end of treatment visit, for the weighted subscale scores and the total score, will be analyzed using the same ANCOVA approach as specified in Section 5.5.3.2.4.

Missing data will be handled according to Section 5.1.1.2.2.

The QOLIE-31-P was to be completed for patients aged 19 years and above only. The primary analysis will be based on all patients who have a completed questionnaire, regardless of age. Summaries and analyses will be repeated using questionnaires only from patients who were aged 19 years or older at the time of informed consent.

The individual responses will not be listed, only the derived information for each derived score will be listed.

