5.1.1.2.2 Quality of Life in Epilepsy, Version 2 (19 Years and Above)

For missing questions within subscales, the following rule will be applied:

- For subscales containing 4 or more questions (not including the 'distress' item), apply the following:
 - If less than or equal to 50% of the questions within the subscale are missing then the converted score for the missing questions will be set to the average of the non-missing question converted scores.
 - If more than 50% of the questions within the subscale are missing then the subscale weighted score will be set to missing.
- For subscales containing less than 4 questions (not including the 'distress' item) the subscale weighted score will be set to missing.

For missing 'distress' items, the following rule will be applied:

- If the corresponding subscale weighted score is missing then no imputation is needed and the 'distress' item converted score will be missing.
- If the corresponding subscale weighted score is not missing then set to the average of the non-missing 'distress' item converted scores.

For missing subscale weighted scores or missing 'distress' item converted scores, the following rule will be applied when calculating the total score:

- If 3 or more of the 'distress' item converted scores are missing then the total score will be set to missing.
- If 3 or more of the subscale weighted scores are missing then the total score will be set to missing.

- If less than 3 'distress' item converted scores are missing and less than 3 subscale weighted scores are missing, then the total score will be calculated based on the available non-missing data, following the rules above.

Note: it is possible that a subscale weighted score is missing, but that the corresponding 'distress' item was answered and the converted score is not missing. Following the rules above, the total score would include the non-missing 'distress' item converted score in the calculation even though the corresponding subscale weighted score is missing and hence not included.

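### The printed QOLIE-31-P total runs 0–10,000 against a stated 0–100, and an answered distress item for a missing subscale stays in the denominator and pulls the total down

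*SAP*

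**What the plan says.** SAP section 5.5.3.2.5 sets out the scoring in three steps.

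- Scale of the inputs: "The raw score for each question and the 'distress' item are converted to a 0-100 score".
- Subscale weighted score: "Sum of converted scores for each question in the subscale", divided by the number of questions, then multiplied by that subscale's distress score. There are seven subscales, each with one distress item.
- Total: "Sum of all subscale weighted scores" divided by the sum of the distress scores, then multiplied by 100. The sentence introducing this reads "The total score (ranging from 0 to 100) is then calculated as".

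The weighted subscale scores and the total are both summarized by visit, and their changes from baseline to end of treatment are analyzed by ANCOVA.

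SAP section 5.1.1.2.2 covers missing data. The total is set to missing when three or more weighted scores, or three or more distress scores, are missing; otherwise it uses what is available. A closing Note takes the case of a missing subscale whose distress item was answered. It says that the total includes the non-missing distress "item converted score in the calculation even though the corresponding subscale weighted score is missing and hence not included".

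**The concern.** There are two separate problems.

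First, the formula and the range stated for it cannot both be right. If the formula is programmed as printed, every reported mean, treatment difference and confidence limit for the total is 100 times the scale given to the reader.

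Second, distress scores enter the total on their own only through the denominator. Under the Note, a missing subscale adds its weight there and nothing to the numerator. The result is no longer a weighted mean of the available subscales; the missing subscale is in effect scored as zero quality of life. If the gap is present at one of the two visits only, the change score moves although the patient has not changed: down if the gap is at end of treatment, up if it is at baseline.

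The case can arise easily. In subscales with fewer than four questions (not counting the distress item), section 5.1.1.2.2 imputes nothing, so a single skipped question makes the weighted score missing. The SAP handles the childhood instrument differently: section 5.1.1.2.1 averages the QOLCE subscale scores that are present.

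**Working it through.** **Inputs** (SAP 5.5.3.2.5 and 5.1.1.2.2): seven subscales; subscale mean `m_j` on 0–100; distress score `d_j` on 0–100; a total is still computed with up to two subscales missing.

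**Step 1: the stated range.** As printed,

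- weighted score `w_j = m_j × d_j`, which runs 0–10,000;
- total = [sum(`w_j`) / sum(`d_j`)] × 100.

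The bracket is a weighted mean of the `m_j`, so it already lies on 0–100. With everything at 100: 7 × (100 × 100) / (7 × 100) × 100 = 10,000. With every `m_j` at 0, 50 or 100 and any common non-zero distress score, the totals are 0, 5,000 and 10,000. The stated maximum of 100 is not reproduced.

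Variants tried:

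| Variant | Range of total |
|---|---|
| As printed | 0–10,000 |
| Distress on 0–1 throughout | 0–10,000 (the scale cancels) |
| Final × 100 dropped | 0–100 |
| Each weighted score divided by 100, final × 100 kept | 0–100 |

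Multiplying the response and its baseline by the same constant multiplies estimates and confidence limits by 100 and leaves ANCOVA p-values as they are.

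**Step 2: a missing subscale with its distress item answered.** The rest is on the 0–100 scale. Let subscale k be missing. The sound score is sum(m d)/sum(d) over the six others. The SAP rule keeps `d_k` in the denominator. Relative to the sound score it gives a factor

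1 − `d_k` / sum(d), with the sum over all seven distress scores.

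At equal distress scores the loss is 1/7 = 14.3% for one missing subscale and 2/7 = 28.6% for two.

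Example: every `m_j` = 60 and the other distress scores 50, so the sound score is 60.0.

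| Missing | Distress score of missing subscale | SAP score | Loss in points |
|---|---|---|---|
| One | 25 | 6 × 60 × 50 / 325 = 55.4 | 4.6 |
| One | 50 | 6 × 60 × 50 / 350 = 51.4 | 8.6 |
| One | 100 | 6 × 60 × 50 / 400 = 45.0 | 15.0 |
| Two | 50 each | 5 × 60 × 50 / 350 = 42.9 | 17.1 |

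If the distress item is missing as well, neither term enters and the loss is zero.

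**Step 3: variation between patients.** The documents give no distribution of distress scores. As an assumption, each was drawn independently and evenly from 0, 25, 50, 75 and 100. The mean loss is then 14.2% for one missing subscale (5th to 95th percentile 0% to 31%) and 28.5% for two (7% to 50%).

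**The case against.** The factor of 100 can fairly be called an editorial slip. The same sentence states the intended range, output above 100 would be noticed, the programmed code may already be right, and no p-value depends on it. All of that stands. It limits the consequence but does not remove the contradiction. The weighted subscale scores, which have no stated range and are analyzed in their own right, would not show the problem so plainly.

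The Note describes its case openly, so the rule is deliberate, and it may follow the cited scoring manual, which is not available here. That is a reason to check the manual before changing the rule. But the SAP gives no reason for the rule and does not mention the downward shift.

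Several stronger readings are tempting and should not be drawn:

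- That every missing subscale costs one seventh. This holds only at equal distress scores and only when the distress item was answered. In subscales with four or more questions, imputation when up to half are missing makes the case rarer, and nothing in the documents says how often it would arise.
- That the false change is as large as a real treatment effect. Neither document gives an expected effect, standard deviation or meaningful difference for this instrument.
- That the comparison between arms is biased. That would need the gaps to differ by arm or by visit within arm. With similar gaps in each arm the rule mainly adds noise.

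**Conclusion.** Both defects hold on the SAP's own text, and no other section corrects either.

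The printed total runs 0–10,000 against a stated 0–100. This affects the scale of reported estimates, not inference.

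The missing-subscale rule can affect inference through individual change scores. Its size is `d_k`/sum(d) of the sound score, up to two subscales can be affected, and it arises only where the distress item was answered. The 60-point patient and the drawn distress scores are illustrations, not estimates for this trial.

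A reader might infer that the trial's main conclusions are at risk. They are not: QOLIE-31-P is one of the other secondary endpoints, intended for patients aged 19 and over, and lies outside the eight-test hierarchy in SAP section 5.5.1. The point should be corrected because the rules give a wrong result if followed as written.

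**What to change.** 1. In section 5.5.3.2.5, make the formula agree with 0–100 in one of two ways: drop the final × 100, or divide each subscale weighted score by 100 and keep the × 100. The first leaves the separately analyzed weighted subscale scores on 0–10,000; the second puts them on 0–100 too. Moving distress to 0–1 in both numerator and denominator is not a remedy, because the scale cancels.
2. In section 5.1.1.2.2, sum the distress scores only over subscales whose weighted score is in the numerator, and delete the Note.
3. Check both changes against the scoring manual cited in the SAP. If the manual requires the rule in the Note, say so, state the downward shift, and add a sensitivity analysis using the matched denominator.

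The cost is two lines of SAP text and one scoring step, with no change to data collection.

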5.5.3.2.6 Physician Global Impression of Change

Blinded Phase:

The PGIC comprises the following questions to be rated on a 7-point scale:

- Please assess the change in the patient's general functional abilities since Visit 3 (prior to the commencement of study medication).

The possible responses are: Very Much Improved; Much Improved; Slightly Improved; No Change; Slightly Worse; Much Worse; Very Much Worse.

The responses above are based on comparison with a brief description of the patient's overall condition used as a memory aid from Visit 3.

Each response will be coded with a score from 1 to 7, where 1 = Very Much Improved, and 7 = Very Much Worse.

The PGIC response/score, recorded at each visit, will be summarized separately, on both a categorical and continuous scale, by treatment arm.

The score at the end of treatment visit and last visit (if different to the end of treatment) will be analyzed using ordinal logistic regression. Proportional odds modelling will be carried out by including treatment arm as a factor. The estimated odds ratio (GWP42003-P vs. placebo), 95% CI for the odds ratio, and the p-value testing the null hypothesis that the odds ratio is equal to 1, will be presented. Analysis performed at the last visit will be considered the primary analysis for this endpoint, with the analysis at the end of treatment visit considered a sensitivity analysis.

Should the proportional odds assumption not hold, i.e. if the p-value for the score test for proportional odds assumption is <0.05, then, as a sensitivity analysis, the scores will also be analyzed using a Cochran-Armitage trend test. This will be presented together with the results of the ordinal logistic regression.

Open-label Extension:

Descriptive summaries described above for the blinded phase will be repeated for OLE visits.

5.5.4 Exploratory Efficacy Endpoints

5.5.4.1 Composite Focal Seizure Score

Blinded Phase:

Composite focal seizure score will be calculated as the sum of:

- 1 × Number of focal motor seizures without impairment of consciousness or awareness.
- 2 × Number of focal seizures with impairment of consciousness or awareness.
- 3 × Number of focal seizures evolving to bilateral convulsive seizures.

Summaries and analyses of composite focal seizure score will be performed as per the primary endpoint (Section 5.5.2).

Sensitivity analyses will be performed on the ITT analysis set, repeating the above analysis, using data for only the maintenance period, titration period, and during each 4 weeks of the

maintenance period (Week 1 to 4, Week 5 to 8 and Week 9 to 12 of the 12 week maintenance period).

Analyses on the maintenance period, titration period and by each 4 weeks of the maintenance period will include only patients who have at least 7 days of seizure data within each period.

Open-label Extension:

Summaries will be performed for the OLE periods as described in the OLE portion of the primary endpoint section (Section 5.5.2).

5.5.4.2 Individual Seizure Types

Blinded Phase:

For each individual seizure type (focal motor seizures without impairment of consciousness or awareness, focal seizures with impairment of consciousness or awareness, focal seizures evolving to bilateral generalized convulsive seizures, tonic-clonic, tonic, clonic, atonic, absence, myoclonic and partial sensory seizures, and infantile or epileptic spasms), summaries will be performed as per the primary endpoint (Section 5.5.2). However, analyses will only be performed for the following seizure types:

- Focal motor seizures without impairment of consciousness or awareness;
- Focal seizures with impairment of consciousness or awareness;
- Focal seizures evolving to bilateral generalized convulsive seizures;
- Tonic-clonic; and
- Tonic.

Patients with no seizures during the baseline period, for a particular seizure type, will be excluded from the analysis of that seizure type.

Sensitivity analyses will be performed on the ITT analysis set, repeating the above analyses using data for only the maintenance period, titration period, and during each 4 weeks of the maintenance period (Week 1 to 4, Week 5 to 8 and Week 9 to 12 of the 12 week maintenance period).

Analyses on the maintenance period, titration period and by each 4 weeks of the maintenance period will include only patients who have at least 7 days of seizure data within each period.

Individual seizure type responders and freedom will also be summarized and analyzed using the methods described in Section 5.5.3.2.1, for the following seizure types only:

- Focal motor seizures without impairment of consciousness or awareness;
- Focal seizures with impairment of consciousness or awareness;
- Focal seizures evolving to bilateral generalized convulsive seizures;
- Tonic-clonic; and
- Tonic.

The summaries and analyses during the maintenance and titration periods and during each 4 weeks of the maintenance period will be produced. Patients with no corresponding seizures, for a particular seizure type, during the baseline period will be excluded from the analysis for that seizure type.

Open-label Extension:

Descriptive summaries described above for the blinded phase will be repeated for OLE periods.

